9.18.7 Maternal health questionnaire

The questionnaire for the mother will cover self-reported incident conditions, i.e. illnesses.

It will also assess symptoms of anxiety and depression using the PHQ-2 survey, which has 2 questions with Likert responses. The PHQ-2 survey has been translated and validated in Chichewa and Swahili, Hindi, Kannada, Marathi, and Oriya. An extended list of questions will be asked at 9 and 12 months and a shortlist may be asked during the phone calls.

9.18.8 Follow up phone survey

(Insert local partner name if applicable)

In order to minimize loss to follow up, there will be additional touch points between the 6- and 9-month visit (at around 7.5 months) and the 9- and 12-month visits (at around 10.5 months). This will be done in the form of a phone call. These calls will last approximately 15-20 minutes.

Where a participant cannot be reached after numerous attempts, a home visit may be made. A short survey will be administered at these touch points asking mainly about the status of the infant and mother and about feeding.

9.19 Ethics

9.19.1 Risks to participants

This study does not involve an experimental treatment or intervention. It does involve identification of a vulnerable population of infants who are low birthweight and who are nutritionally at risk given anthropometrics and growth trajectory. These patients will be managed per the current SOC and routine processes at each study site. A goal of this study is to gain better understanding about the SOC for management of this population. We anticipate that the SOC will vary by site.

The risk to subjects will be minimized through adherence to local SOC. When an infant is identified as at risk, they will be referred to health officials to receive the local SOC feeding therapies. For the prospective cohort, will continue to follow enrolled participants through 12 months postpartum, including if the infant is admitted to a facility.

The proposed study activities pose minimal, if any, added health risk to study participants. The population in this study is intrinsically at high risk for morbidity and mortality due to underlying LBW, but we do not anticipate that the study would contribute to these underlying risks.

Because HIV positive mothers will be eligible for inclusion in the study, the risk of mother-to-child transmission will exist. However, HIV testing and treatment among pregnant women is high in the study sites, and thus the risk of transmission of HIV through breastfeeding is low.

Less severe risks may include burden of travel and loss of economic productivity for families enrolled in the prospective cohort who report to the clinics for follow-up, as clinic attendance may be costly from both a monetary and time perspective

There could also be inconveniences or experience discomfort in direct observation of feeding practices immediately after childbirth and subsequently. We will mitigate this by obtaining informed consent, emphasizing the right to opt out at any time, and employing female observers and providers.

9.19.2 Informed consent

The informed consent process for each of the data collection streams is described in their respective sections of this protocol.

9.20 Data analysis

As most of the quantitative data collected is being used for descriptive epidemiology of LBW infants, we will use means, medians and standard deviations to describe continuous variables. Categorical variables

will be analyzed with frequencies and proportions, as appropriate. Confidence intervals around all measures will be constructed to take any clustering into account.

For anthropometric analyses, we will use the INTERGROWTH charts to describe growth velocity and trajectories for the infants, including stunting (length-for-age z-score, LAZ), underweight (weight-for-age z-score, WAZ), and wasting (weight-for-length z-score, WLZ). To determine Z-scores, we will use the INTERGROWTH-21st standards for preterm infants (<37 weeks gestation), and the WHO postnatal growth standards for term infants (>37 weeks gestation) (Villar et al 2015).

Where possible, we will relate these anthropometric measures with reported infant feeding, using correlations for continuous variables or cross-tabulations of categorical variables. Any further analyses will be post-hoc and described separately.

6-month extension:

As with the original LIFE study, we will utilize mixed methods to fully understand the growth trajectories and care for LBW infants during the first 12 months of life. We will use the full cohort from 0 to 12 months of age to assess growth trajectories and velocities over time, evaluating the impact of complementary feeding (food types and timing) on infant anthropometrics, and assessing morbidities over time.

We will use descriptive methods for initial description of the LBW cohort with means, medians and standard deviations for continuous variables. Categorical variables will be analyzed with frequencies and proportions, as appropriate. Confidence intervals around all measures will be constructed to take any clustering into account.

For anthropometric analyses, for preterm infants we will use the INTERGROWTH-21st postnatal growth standards for preterm infants to describe growth velocity and trajectories for the infants up to 12 months of age, including stunting (length-for-age z-score, LAZ), underweight (weight-for-age z-score, WAZ), and wasting (weight-for-length z-score, WLZ). To determine Z-scores, we will use the INTERGROWTH-21st standards for preterm infants (<37 weeks gestation), and the WHO postnatal growth standards for term infants (>37 weeks gestation).

We will use longitudinal multilevel models to assess the contribution of infant feeding and morbidity as well as maternal and household characteristics. Such models will also allow us to test whether there are differences in growth patterns related to gestational age and size for gestational age at birth, and whether the effects of care, feeding, and morbidity differ according to birth characteristics.

10 Qualitative research

As shown in Table 8, we will conduct FGDs and/or IDIs with a variety of stakeholders including clinicians, first-time and experienced mothers, family members, religious leaders, community leaders, traditional health care providers, supply chain and milk bank experts, and Ministry of Health officials. We might also speak with individuals that have been identified through the interviews as having a specific set of expertise or experience relating to the domains below. We recommend a minimum and maximum number of FGDs or IDIs for each of the populations that allows sites flexibility for religious leaders, community leaders, and traditional healers based on their context and which group is the most appropriate

to approach for these discussions. Each discussion will cover the domains listed – as well as others as they arise – corresponding directly to one or more of our study objectives.

Table 8: Focus groups and in-depth interviews, with domains for discussion

Focus group discussions	8-12 total	Domains for discussion	Meets objective		
			1	2	3
Mothers of preterm LBW infants aged 0-3 months	1				
Mothers of full-term LBW infants aged 0-3 months	1	Beliefs and norms around IYCF practices Feasibility and acceptability of IYCF options Preferences around IYCF support	✓	✓	
Mothers of preterm LBW infants aged 4-7 months	1	Barriers and facilitators to IYCF			
Mothers of full-term LBW infants aged 4-7 months	1				
Male family members of LBW infants	1-2	Beliefs and norms around IYCF practices Feasibility and acceptability of IYCF options	✓	✓	
Female family members of LBW infants	1-2	Role of family and community in IYCF practices			
Religious leaders		Beliefs and norms around IYCF practices Barriers and facilitators to IYCF implementation			
Community leaders	2-4	Feasibility and acceptability of IYCF options Religious and community leaders only: Role of religious or community leaders in IYCF Religious or community beliefs and rules around IYCF	✓	✓	
Traditional healers					
Health Care Workers: Nurses, nurse midwives, midwives	8-20	Current SOC for LBW infants Feasibility and acceptability of IYCF options Barriers and facilitators to IYCF implementation Prior IYCF strategies and lessons learned	✓	✓	
In-depth interviews	38-84 total	Domains for discussion	1	2	3
Health Care Workers: Doctors	8-20				
Community health workers	8-20	Current SOC for LBW infants Feasibility and acceptability of IYCF options Barriers and facilitators to IYCF implementation Prior IYCF strategies and lessons learned	✓	✓	
MOH and other govt. officials	2-4	Commitment to LBW infant feeding strategies Possible risks and their mitigation Prior IYCF strategies and lessons learned	✓	✓	

		Recommendations for implementation		
Supply chain experts	2-4	How BMS and bottled water can be distributed reliably in the community How external factors affect the supply chain Barriers and facilitators to a reliable supply chain		✓
Human milk bank experts	2-4	How DHM can be distributed reliably in the community How external factors affect the supply of DHM Barriers and facilitators to establishing human milk banks		✓
In-depth interviews(extension)	16-20 total	Domains for discussion	1	2 3
Mothers of LBW infants aged 9-12 months, male, growing well	4			
Mothers of LBW infants aged 9-12 months, female, growing well	4	Feeding practices Home environment Maternal and infant well-being Growth of infant	✓	✓
Mothers of LBW infants aged 9-12 months, male, not growing well	4			
Mothers of LBW infants aged 9-12 months, female, not growing well	4			

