9.5 Replacement of infants who die in the first 72 hours

As described in the exclusion criteria for the prospective cohort, it will not be possible to identify all infants with severe or critical illness before discharge. Because not all diagnoses can be made definitively before discharge, some critically ill infants may end up in the prospective cohort, and may, unfortunately, die early.

These cases will not contribute much data to the study on their growth and feeding patterns, and may erode our ability to achieve our target sample size. We aim for 350 mothers at enrollment with 300 still

enrolled at 6 months. The drop of 50 mothers is due to expected loss to follow up as well as deaths. However, this margin may not be large enough to cover all the deaths if we include infants who have serious illnesses that are not apparent at discharge. In that case, we may end up with more infants than expected dying in the first few days, and fewer than 300 infants by six months.

For these reasons, we will consider an enrolled infant who dies within the first 72 hours to be excluded from the cohort, and we will recruit an additional infant in its place. In effect, this puts an additional inclusion criterion on this cohort, which is surviving the first 72 hours of life. If the infant dies at any time after 72 hours, he or she will not be replaced in the sample.

Baseline data from infants who die in the first 72 hours will not be included in the formal analyses, but may be included in post-hoc explorations.

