9.11 Maternal or infant death during study period

In the case of a maternal death during the study period, we will ask permission from the family to continue following the infant. A new informed consent process will be conducted with the infant's primary caregiver.

[figure not shown]
In the case of an infant death during the study period, we will not continue to collect study information on the mother; however, we will ensure that the mother is receiving adequate care, through appropriate referral mechanisms.

Verbal autopsies of the infant would be desirable, but they were not budgeted for as part of this study. In Tanzania, the study team will have to perform a verbal autopsy at 40 days post-death to meet government regulations, so they will be available for that site. If possible, we will gather information from verbal autopsies.

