9.18.5 Infant feeding questionnaire

We will administer baseline and follow-up questionnaires on infant feeding/maternal lactation. An extended list of questions will be asked at 9 and 12 months and a shortlist may be asked during the check in phone calls. The infant feeding questionnaire will cover topics such as:

Description of feeds

- Feeds provided:
 - Breastmilk (Mother's own milk, Other mother's milk -), colostrum (at baseline), Donor Human Milk
 - Formula
 - Supplements
 - Other feeds (water, cow's milk, etc.)
 - Liquids
 - Semi solid / solid foods and specific food groups
- Method of feeding (direct breastfeeding, cup/palladai/spoon, bottle)
- Who advised/decided on the type of feed (clinic staff, mother, etc)
- Provider of feeds (mother, clinic staff, etc.)
- Timing of introduction of complementary feeds and reasons
- Frequency of feeds
- Self-efficacy of complementary feeding

Breastfeeding (this information will not be collected during the extension as it is not applicable anymore):

- Time to first latch or milk feed (global standard: within 1 hour of birth)
- Day (post-birth) achieved full milk production/established lactation (“coming to volume”)
- Exclusive breastfeeding duration
- Number of breastfeeding or expression sessions per 24 hours
- Expressed Breast Milk storage method (refrigerator, freezer, etc.)
- Breastfeeding adequacy measures, like frequency of feeds (average number of expressions/full breastfeeding episodes per day), duration of feeds, and direct observation if the infant breastfeeds during the interview (WHO IMCI criteria, LATCH score, PIBBS scale). In addition, we will use the NeoEAT-Breastfeeding Screener Tool to assess symptoms of problematic infant breastfeeding based on maternal self-report.
- Maternal Perceived milk insufficiency (PMI)
- Incidence of infection (e.g. mastitis) or troubles breastfeeding (e.g. engorgement)
- Reason for stopping/difficulty breastfeeding (e.g. mother decision; medically directed)
- Breastfeeding self-efficacy and social support
- Use of kangaroo mother care; separation of mother and infant
- IYCF support provided/program/education availability
- Influence of family/friends (social norms) on breastfeeding behavior

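### Exclusive breastfeeding duration is cut off by loss, death and the 6-month end of collection, but the plan offers only raw means, medians and SDs, which can give a substantially short figure

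*Combined protocol and SAP*

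**What the plan says.** Section 9.18.5 lists "Exclusive breastfeeding duration" among the breastfeeding topics of the cohort questionnaire. Of that block it says that "this information will not be collected during the extension as it is not applicable anymore", so the item is last asked at 6 months. Section 2 defines exclusive breastfeeding as a feeding status, but no section defines its duration: when it starts, what ends it, or whether it is capped.

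Section 9.5 says "We aim for 350 mothers at enrollment with 300 still" enrolled at 6 months, and adds: "The drop of 50 mothers is due to expected loss to follow up as well as deaths". Section 9.11 says: "In the case of an infant death during the study period, we will not continue to collect study information on the mother".

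For analysis, Section 9.20 says "we will use means, medians and standard deviations to describe continuous variables". The extension part of 9.20 repeats the rule. Categorical variables get frequencies and proportions, intervals are to allow for clustering, and any further cohort analysis is left post hoc. The longitudinal multilevel models planned for the extension concern growth. The documents give no censoring rule, time-to-event method or handling of death for any feeding duration.

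**The concern.** EBF duration is a time to an event. If an infant is still exclusively breastfed when lost, withdrawn or last asked at 6 months, the stop has not been seen and the recorded time is a lower bound. If the infant dies while exclusively breastfed, the stop will never occur. A raw mean or median has no place for such values, so the analyst must drop them or treat them as complete. Both choices pull the figure down.

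Objective 2 covers lack of success on mother's own milk. Section 2.1 says the LIFE data, including breastfeeding behaviours, will inform the later trial's definition of infants for whom breastfeeding is insufficient. Sites are analysed separately, so different EBF or loss rates could produce site differences that come from the summary and not from practice. Section 3 says that exclusive feeding rates in LBW infants are not well known, so a short figure would be hard to spot from outside.

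**Working it through.** **The plan's own figures.** The documents give no figure for EBF duration. Those they do give reproduce: attrition is 50/350 = 14.3%, and the precision example in Section 9.12 is 1.96 × √(0.05 × 0.95/250) = 0.027, the stated ±2.7%.

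**Inputs**
- Attrition by 6 months: 1/7 = 14.3% (Section 9.5).
- End of the breastfeeding block: 6 months (Section 9.18.5).
- Share still EBF at 6 months, S(6): not given for LBW infants. Assumed 38%, borrowing the global all-infant figure in Section 3, with a range of 20% to 60%.
- Assumed: constant stopping rate; loss even over 0–6 months and unrelated to feeding; deaths not separated from other loss.

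**Base case, S(6) = 0.38**
1. Stopping rate λ = −ln(0.38)/6 = 0.1613 per month.
2. True median = ln 2/λ = 4.30 months. True mean restricted to 6 months = (1 − 0.38)/λ = 3.85 months.
3. Probability of not yet being lost at month t: G(t) = 1 − (1/7)(t/6) = 1 − t/42.
4. Share with an observed stop = 0.62 − (1/42)(3.845 − 6 × 0.38) = 0.62 − 0.037 = 0.583, so 41.7% of durations are incomplete.
5. Observed stops only: half of 0.583 is 0.291. By t = 2.20 the observed stops amount to 0.299 − 0.007 = 0.291, so the median is 2.20 months, 49% short.
6. Last contact as the stop: solve exp(−λt)(1 − t/42) = 0.5. At t = 3.72 this is 0.549 × 0.911 = 0.500, so the median is 3.72 months, about 13% short.

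**Range.** Medians in months from 2 million simulated infants. Paired values are for loss at a constant rate and for all loss in the first 6 weeks, lower value first.

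| Still EBF at 6 months | True | Observed stops only | Last contact as stop | Followed to 6 months, capped at 6 |
|---|---|---|---|---|
| 20% | 2.58 | 1.81–1.82 | 2.01–2.36 | 2.58 |
| 38% | 4.30 | 2.20–2.22 | 3.35–3.71 | 4.30–4.31 |
| 60% | beyond 6 | 2.52–2.55 | 6.00 (the cap) | 6.00 (the cap) |

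Means behave the same way. At 38%, last contact as the stop gives 3.40–3.61 and observed stops only about 2.45, against a restricted mean of 3.85. Kaplan-Meier on the same data returns 4.30 and 3.84.

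**Effect of retention (S(6) = 0.38, even loss)**

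| Loss by 6 months | Last contact as stop | Observed stops only |
|---|---|---|
| 0% | 4.30 | 2.30 |
| 14.3% | 3.72 | 2.20 |
| 35% | 3.07 | 2.04 |

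Under both handlings, better retention brings the median closer to 4.30.

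**The case against.** **The averaging is inferred.** EBF duration is one topic in a questionnaire list, and 9.20 does not name it. Section 9.12 says the main results are rates with confidence intervals, so reporting the percent still EBF already fits the plan, and a Kaplan-Meier median is itself a median. This stands as a limit: no planned result is shown to be biased. But 9.20 covers continuous variables without exception and gives no way to handle an incomplete one.

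**Another handling works.** Infants followed to 6 months, capped at 6, give the right restricted mean, and the right median if more than half stop earlier. That holds only when loss is unrelated to stopping. If mothers who stop early are lost more often, the figure is too long. The plan does not specify this handling.

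**The 6-month cut-off is partly harmless.** Section 3 cites a recommendation of six months' exclusive breastfeeding, so a 6-month cap is a sensible target, and the cut-off alone does not bias a median reached earlier. Section 9.18.5 also lists "Timing of introduction of complementary feeds and reasons" outside the dropped block and says: "An extended list of questions will be asked at 9 and 12 months and a shortlist may be asked during the check in phone calls". Some later stops could therefore be dated. Neither point helps with infants lost or dead before 6 months.

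**Stops fall between visits.** Table 7 goes from 4 to 6 months, so stop dates may be interval-censored, which can shift a figure either way. The fix allows for this.

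**Readings that go too far.** A reader might infer that the reported duration will be too short; that depends on a handling the plan leaves open. A reader might infer that the distortion grows with better retention; the last table shows the reverse. A reader might take EBF duration to be what the study exists to measure; Section 4 gives a broader goal, and the key outcomes it names are growth, morbidity and lack of success on mother's own milk.

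**Conclusion.** The point holds in a limited form and should be fixed before analysis. EBF duration is right-censored by loss and by the end of the breastfeeding block, and cut short by death. The only summary the plan offers does not suit such a variable and can give a substantially short figure. In the base case the median is 2.2 months from observed stops only, or 3.7 with last contact as the stop, against a true 4.3.

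These sizes are illustrative. Only the 14.3% attrition and the 6-month end of collection come from the study's own design. The 38% refers to all infants worldwide in the first six months, not to LBW infants still EBF at 6 months. The constant stopping rate and the even, unrelated loss are assumptions. The larger gap belongs to a handling that the plan neither proposes nor rules out.

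**What to change.** In Section 9.20, exempt EBF duration, and other times to stopping or switching a feed, from the mean, median and SD rule. Then:

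- Define EBF duration: its start, what counts as a stop, and a cap at 6 months.
- Report the percent still EBF at each visit.
- Add a time-to-event median (Kaplan-Meier, or interval-censored where stops are known only to fall between visits) or a mean restricted to 6 months. Where fewer than half have stopped by 6 months, report the median as not reached.
- Censor at the last contact at which the infant was still EBF. Treat death as a competing event, not as ordinary censoring.
- Give intervals that allow for twins, as 9.20 already asks for clustering.
- Do not report a mean or median over observed stops only.

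This method also assumes that, among infants still EBF, loss is unrelated to stopping. Unlike an analysis of infants followed to 6 months, it keeps stops seen before a mother was lost. The cost is a short addition to 9.20 and a little more analysis work. No new data are needed.

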Globally, 15% of all babies, amounting to 20 million infants each year, are born low birthweight (LBW). Compared to normal weight infants, LBW infants are at higher risk of morbidity, mortality, and poor growth (Risnes et al 2011; Larroque et al 2001; WHO 2006). The main causes of LBW are preterm birth, intrauterine growth restriction (IUGR), or their combination. Preterm birth and IUGR may have different causes, and these conditions may carry different risks for morbidity, mortality, sub-optimal feeding and growth (Katz et al 2013; Christian et al 2013). LBW contributes directly or indirectly to 60-80% of neonatal deaths (WHO 2011; Lawn et al. 2014). It is such an urgent issue that the World Health Assembly set out to reduce LBW by 30% by 2025 (WHO 2014). Unfortunately, there is a paucity of information around feeding practices and optimal feeding strategies for this population, particularly for LBW infants who struggle with breastfeeding or growth.

In 2011, the World Health Organization released the Guidelines on Optimal Feeding for Low Birthweight Infants in Low-and Middle-Income Countries (LMICs). However, 70% of the guidelines are based on “low or very low” quality of evidence (WHO 2011), and the majority of research regarding mother’s own milk (MOM) alternatives has been in high-income, hospital-based settings (Blencowe 2013). There is a pressing lack of information about LBW infants in LMICs: existing feeding patterns; rates and causes of unsuccessful breastfeeding; and effective options for feeding, fortification, or supplementation with micronutrients. Forty global health organizations recently issued an urgent call to action to improve the evidence base, specifically for neonatal care units (Greenslade et al 2017). This study hopes to address some of these key gaps.

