9.18.2 Gestational age (baseline visit only)

Measuring gestational age is notoriously difficult. Prematurity and intrauterine growth restriction are the primary causes of LBW. We anticipate that there will be physiologic differences between these groups, but also acknowledge the challenges in accurate identification of gestational age in this study population due to limitations in prenatal care and use of early ultrasound. The availability and quality of gestational age data will be highly variable between study sites. Only one site (India-Karnataka site) will have access to early pregnancy ultrasonography, because of the presence of an existing trial for antenatal corticosteroid. In the remaining sites, the majority will likely not have access to ultrasound dating and will rely on last menstrual period (LMP) or Symphysis fundal height, as per standard of clinical care. We will capture what gestational age information is available from the woman's antenatal card, ultrasound history, etc. In cases where ultrasound data is available (either through clinic records or maternal self-report), we will consider this to be the first preference for gestational age dating. We will also ask the mother the date of her last menstrual period (LMP), and use this information as second preference for gestational age dating if ultrasound results are not available.

Given the poor quality and availability of antenatal dating in some sites, the LIFE study will also need to rely on neonatal assessment for gestational age dating. In a recent systematic review, 18 different neonatal assessments for gestational age dating were identified in the literature (Lee 2017). The most commonly used, simpler and feasible assessments, such as the Ballard or Capurro, were inaccurate, dating pregnancies to +/- 4 weeks of ultrasound dating. The Dubowitz exam was found to be the most accurate, dating 95% of pregnancies within +/- 2.6 weeks of an

ultrasound based date. However, the Dubowitz exam includes 21 signs including neurologic and external physical signs, and the feasibility of training, standardization and use in LMIC requires further programmatic research.

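### The only pre-specified 0–6 month feeding–growth analysis is crude, so differences in size or maturity at birth may be read as feeding differences

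*Combined protocol and SAP*

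**What the plan says.** Section 9.20 (Data analysis) describes the original cohort first. Where possible, "we will relate these anthropometric measures with reported infant feeding, using correlations for continuous variables or cross-tabulations of categorical variables". The next sentence closes the list: "Any further analyses will be post-hoc and described separately". No covariate or stratifier is named. The anthropometric measures meant are growth velocity and trajectories and the length-for-age, weight-for-age and weight-for-length z-scores. Preterm infants are scored on one growth standard and term infants on another.

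The baseline information exists. Newborns are weighed at screening (9.1), gestational age is determined at baseline (9.18.2), infant anthropometry is taken at baseline (Table 7), and section 2 defines three LBW bands. Section 9.20 uses none of the bands.

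The protocol itself regards status at birth as important. Of preterm birth and growth restriction, section 3 says "these conditions may carry different risks for morbidity, mortality, sub-optimal feeding and growth". On the same two groups, 9.18.2 says "We anticipate that there will be physiologic differences between these groups".

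The extension part of 9.20 goes further. "We will use the full cohort from 0 to 12 months of age to assess growth trajectories and velocities over time", and then "We will use longitudinal multilevel models to assess the contribution of infant feeding and morbidity as well as maternal and household characteristics". These models are also to test "whether there are differences in growth patterns related to gestational age and size for gestational age at birth", and whether the effects of feeding vary with birth characteristics.

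**The concern.** A baseline factor related both to how an infant is fed and to how it grows confounds a crude comparison of growth between feeding groups. Section 3 names such a factor in cautious terms, and the plan collects it but does not use it in the only 0–6 month feeding–growth analysis that it specifies.

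The results have a use beyond description. Section 3 says the study results will inform feeding strategies and a white paper, and section 2.1 says the data will inform the definition of eligible infants in the follow-on trial. A difference that belongs to birth size, reported as a difference between feeds, could carry into both.

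**Working it through.** **The plan's own figure.** The plan gives no figure for the feeding–growth analysis. The only precision statement is in 9.12, for a single proportion: 1.96 × √(0.05 × 0.95 / 250) = 0.027, so 2.3% to 7.7%. This reproduces, but it says nothing about a two-variable association.

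**Inputs.** From the protocol: about 300 mothers per site (9.12), and 3%–15% of LBW infants stopping or having difficulty breastfeeding within six weeks (section 3). The strengths of association and the shares of infants in each LBW band are not given; the values below are assumptions. Every scenario has no true feeding effect.

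**1. Correlation.** If feeding and growth are related only through birth size, crude r = r(size, feeding) × r(size, growth).

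- Weak: 0.2 × 0.3 = 0.06
- Middle: 0.3 × 0.4 = 0.12
- Strong: 0.4 × 0.5 = 0.20

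With birth size controlled, the correlation is 0. For scale, a 95% interval centred on r = 0 with n = 300 reaches about ±tanh(1.96/√297) = ±0.113. The artefact can be smaller or larger than the sampling error.

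**2. Cross-tabulation.** Assume 15%, 35% and 50% of infants in LBW bands 1, 2 and 3, with no feeding difference in underweight within any band.

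| Feeding difficulty by band | Underweight by band | Overall difficulty | Crude difference in underweight | Odds ratio |
|---|---|---|---|---|
| 8 / 8 / 8% | 60 / 40 / 25% | 8.0% | 0 points | 1.00 |
| 10 / 8 / 6% | 45 / 35 / 25% | 7.3% | 1.6 points | 1.07 |
| 15 / 8 / 3% | 60 / 40 / 20% | 6.6% | 9.9 points | 1.53 |
| 40 / 15 / 5% | 60 / 40 / 20% | 13.7% | 14.0 points | 1.82 |

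Third row worked through:

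- Share with difficulty: 0.15×0.15 + 0.35×0.08 + 0.50×0.03 = 0.0655.
- Underweight among them: (0.0225×0.6 + 0.028×0.4 + 0.015×0.2) / 0.0655 = 0.0277 / 0.0655 = 42.3%.
- Underweight among the rest: (0.33 − 0.0277) / 0.9345 = 32.3%.
- Difference: 9.9 points. With about 20 of 300 infants exposed, the 95% half-width is about 22 points.

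Every overall rate lies within the protocol's 3%–15%.

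**3. Mean z-score, and the sign.** Let Δ be the difference in birth z-score between feeding groups and ρ the correlation of birth with later z-score. The spurious difference is ρΔ for attained z-score and (ρ − 1)Δ for change in z-score. Take 15% exposed (assumed), and let the odds of exposure rise 1.5-fold or 2-fold per SD lower birth z-score (assumed). Then Δ is about −0.40 or −0.65.

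| Odds per SD | ρ | Attained z-score | Change in z-score |
|---|---|---|---|
| ×1.5 | 0.3 | −0.12 | +0.28 |
| ×1.5 | 0.5 | −0.20 | +0.20 |
| ×1.5 | 0.6 | −0.24 | +0.16 |
| ×2 | 0.3 | −0.20 | +0.46 |
| ×2 | 0.5 | −0.33 | +0.33 |
| ×2 | 0.6 | −0.39 | +0.26 |

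At 3% exposed and ρ = 0.5 the attained-score figures are almost the same (−0.20 and −0.34). Adjustment for birth z-score removes the artefact in every row.

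**4. The two parts of 9.20 side by side.** The extension models use the 0–12 month data and bring in birth characteristics. The text says that differences by gestational age and size for gestational age will be tested. It gives no covariate list, does not say that the feeding term is adjusted for birth size, and does not say that these models replace the 0–6 month analysis. The white paper is in the section 15 timeline, labelled 2019–2020. The 9- and 12-month analyses are in the section 15.1 timeline, labelled 2020–2021. The monthly bars are not legible in the available text, so the order rests on the year labels.

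**The case against.** The strongest reply is that the protocol already plans the right analysis: the extension models cover feeding, morbidity and birth characteristics over the full first year, which includes the first six months. This stands in part. A reader might infer from the 0–6 month sentence that confounding by birth status is overlooked everywhere, and the documents do not support that. What remains open is whether feeding is adjusted for birth size, which analysis is to be reported for 0–6 months, and what is available when the feeding strategies are drafted.

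Second, gestational age is not ignored, because it selects the growth standard. That is correct, but it defines the outcome. Birthweight, baseline z-score and size for gestational age remain uncontrolled when feeding groups are compared.

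Third, the analysis is descriptive, and 9.12 plans no hypothesis testing. This stands against judging the plan by false-positive rates or power, and no such figure is used here. It does not remove the bias: 9.20 promises confidence intervals around all measures, and a confounded estimate with an interval can still mislead.

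Fourth, every association strength above is assumed. That is so, and it limits what can be concluded.

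**Conclusion.** The concern holds in a limited form. As written, the pre-specified 0–6 month feeding–growth analysis neither adjusts nor stratifies for birthweight, baseline z-score or gestational age, and differences present at birth may be read as feeding differences.

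A reader might go further and infer that smallness at birth will show up as harm from a type of feed. The documents do not support this. Section 3 says only that the risks may differ, no section says that smaller infants receive particular feeds, and the artefact vanishes if feeding does not vary with birth size. Under the assumptions shown it ranges from 0 to 14 percentage points in underweight, 0.06 to 0.20 in correlation, and −0.12 to −0.39 SD in attained z-score, with the opposite sign for change in z-score. Because the two growth standards differ, bias from prematurity could also mask a real association.

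Nor should the 3%–15% in section 3 be read as a rate of non-exclusive breastfeeding. It refers to infants who stop or have difficulty breastfeeding within six weeks.

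The case for change rests on the plan collecting the relevant baseline values and not using them here, not on any one of these magnitudes.

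**What to change.** In the 0–6 month part of 9.20:

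1. Keep the correlations and cross-tabulations, labelled as descriptive. Show them by LBW band and, separately, by preterm/term where numbers allow. Do not cross the two: with 15% of 300 exposed (45 infants) six cells average 7.5, and with 3% (9 infants) they average 1.5.
2. For each site, pre-specify a linear regression of the 6-week and of the 6-month z-score on feeding category, adjusted for baseline z-score or birthweight and for gestational age, with clustering on mother. Label the result as an association.
3. Alternatively, name these covariates in the extension's multilevel model and state that it is the adjusted analysis for 0–6 months. Any 0–6 month result reported before it should then be marked as unadjusted.
4. Where gestational age is missing or unreliable, give a birthweight-adjusted sensitivity analysis and state which growth standard is applied. A missing category is not a solution: the z-score itself depends on gestational age, and an indicator for missingness can bias the adjusted estimate.

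The cost is about one paragraph of text and a little more programming, with no new data. The downside is sparse strata where few infants are exposed.
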